22.0 Assent of Pediatric Participants

22.1 Select the option(s) that apply to the study:

⊠ Assent of pediatric participants WILL BE SOUGHT following assessment of ability to assent.

Study group(s) to which this method applies: Participants aged 7 and above/deemed able and willing to understand in order to assent

☑ Obtaining assent of pediatric participants is NOT POSSIBLE due to:

- ☑ The capability of the participants (considering the ages, maturity, physical and/or psychological state) is so limited that they cannot reasonably be consulted.
- □ The intervention or procedure involved in the research holds out a prospect of direct benefit that is important to the health or well-being of the participants and is available only in the context of the research.

Study group(s) to which this method applies: Participants under the age of 7/deemed unable to understand in order to assent.

 Obtaining assent of pediatric participants is NOT PRACTICLE given the context of this study (e.g., minimal risk, no direct contact with participants).
 Must complete Addendum B: Waiver/Alteration of Permission/Assent/Consent

22.2 Assessment of Ability to Assent: The study team member conducting the consent discussion will also discuss the study with patients age 7 or older and will check their understanding of the study.

22.3 Assent Discussion: *If seeking assent from pediatric participants, explain how the assent discussion will be conducted. Describe:*

- The assent discussion will take place in conjunction with the informed consent discussion with parents prior to surgery.
- Study team members will inform and reassure patients that they can decide not to participate in the study, and this decision will be respected.
- Patients will be given the opportunity to ask any questions they might have, in addition to any other questions asked by parents.

• Study team members will verify understanding using techniques such as "teach back."

22.4 Documentation of Assent or Inability to Assent: *If seeking assent from pediatric participants, explain how assent, or a determination of inability to assent, will be documented. Describe:*

- CM Research Policy "10.04 Obtaining Permission/ Assent/ Consent" and "Research Documentation in the Electronic Health Record" will be followed.
- E-Consent will be used to document assent.

23.0 HIPAA and Confidentiality

HIPAA regulations apply to this study if the data used or accessed relates to:

- The past, present or future physical or mental health or condition of an individual;
- The provision of health care to an individual; **OR**
- The payment for the provision of health care, AND

identifies the individual or for which there is a reasonable basis to believe it can be used to identify the individual.

23.1 HIPAA Authorization

Select all applicable methods of HIPAA Authorization that apply to this study.

 \boxtimes Full Written HIPAA Authorization will be obtained (within the p/a/c form or standalone form)

⊠ Partial Waiver of HIPAA Authorization (e.g. waiver for recruitment and prescreening purposes only)

Must complete Addendum E: Waiver/Alteration of HIPAA Authorization

□ Alteration of HIPAA Authorization (some but not all required elements of an Authorization are present, e.g. signature will not be obtained) **Must complete** Addendum E: Waiver/Alteration of HIPAA Authorization

a) Describe which proposed elements to be altered.

□ Waiver of HIPAA Authorization (authorization will NOT be obtained)

☑ If Other, explain: We are requesting a Waiver of HIPAA Authorization at age 18 to allow data to continue to be retained in the DSDR without reconsenting former participants who have since turned 18. See Addendum E.

23.2 Specify the PHI for which accessing ("viewing") or recording ("writing down") is necessary for the purpose of this research:

To minimize risks, only the minimum necessary identifiable data should be accessed and/or recorded.

| 1. Name/Initials | □ Accessed only | ⊠ Recorded |
|---|----------------------|----------------------|
| All elements of date (except year) directly related to an individual (e.g. date of birth, admission date, discharge date, date of death) | □ Accessed only | ⊠ Recorded |
| 3. Medical record number | □ Accessed only | \boxtimes Recorded |
| 4. Account number | □ Accessed only | ⊠ Recorded |
| 5. Health plan identification number | □ Accessed only | □ Recorded |
| 6. Social Security Number | □ Accessed only | □ Recorded |
| 7. Device identifiers and serial number | □ Accessed only | □ Recorded |
| 8. Certificate/License number | □ Accessed only | □ Recorded |
| 9. Telephone number | \Box Accessed only | □ Recorded |
| 10. Fax number | □ Accessed only | □ Recorded |
| 11. Email addresses | □ Accessed only | □ Recorded |
| 12. Web addresses (URLs); Internet IP addresses | □ Accessed only | □ Recorded |
| 13. Street address, city, county, precinct, zip code or equivalent geographical codes | □ Accessed only | □ Recorded |
| 14. Full face photographic images and any comparable images | □ Accessed only | □ Recorded |
| 15. Biometric identifiers, including finger and voice print | □ Accessed only | □ Recorded |
| 16. Vehicle identifiers and serial numbers, including license plate number | □ Accessed only | □ Recorded |
| 17. Any other unique identifying number, characteristic or code that may help identify individual participants including their initials (e.g. student or employee ID number) | □ Accessed only | Recorded |
| 18. Elements of date, including year, for persons90 years or older | □ Accessed only | □ Recorded |
| 19. Other: | □ Accessed only | □ Recorded |

The confidentiality of data will be protected by recording data in REDCap securely on the CMH network servers, by allowing access only to study personnel approved by the IRB to work on the study, and by storing Master List identifiers (Name and MRN) on a separate form than the study data.

23.4

No Certificate of Confidentiality will be issued for this study.

24.0 Provisions to Protect the Privacy Interests of Participants*

24.1

The Permission/Assent/Consent discussion will take place in a private room with only the parent(s) and study team members present, to ensure privacy during the P/A/C process.

24.2 Study team members conducting the Permission/Assent/Consent discussion with families will be trained to ensure parents that participation in the study is completely voluntary and not required for their treatment, and to encourage parents to ask questions about the study to help them feel at ease.

24.3 The study team members conducting P/A/C discussions will have access to information about these patients, as they will be encountering them as part of the standard clinical treatment planned for these patients. They will ensure privacy of this information as required for any other clinical information about patients.

25.0 Withdrawal of Participants*

25.1 We do not anticipate any circumstances under which participants would be withdrawn from the study without their consent, however the procedure may change after consenting, either due to surgeon preference of unforeseen circumstances, that would therefore exclude your child from research.

25.2 If a parent chooses to withdraw their child from the study, any data collected about the child will be retained in the study unless the parent requests to have the data excluded from the study.

DATA MANAGEMENT

26.0 Data Collection*

26.1 Data collected during the study will include data about the hernia repair procedure outcome and about the encounter in general (e.g., length of stay, comorbidities impacting length of stay).

26.2 Data will be obtained from the medical record after the hernia repair procedure is completed.

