1.0 Study Summary

| Study Title | Laryngeal mask airway versus endotracheal intubation for | | |
|-------------------------|---|--|--|
| | laparoscopic inguinal hernia repair | | |
| Study Design | Prospective Randomized | | |
| Primary Objective | Evaluate the effectiveness of LMA versus ETT for patients | | |
| | undergoing laparoscopic inguinal hernia repair by | | |
| | measuring SpO2 at 3 standardized timepoints | | |
| Secondary Objective(s) | 1. Evaluate EtCO2 in both groups at three standardized | | |
| | timepoints | | |
| | 2. Evaluate peak airway pressures in both groups at three | | |
| | standardized timepoints | | |
| | 3. Documentation of laryngospasm occurrence in both | | |
| | groups | | |
| Study Population | 12 mo- 8 yo patients undergoing laparoscopic inguinal | | |
| | hernia repair at CMH or CMK | | |
| Study Duration for | Single visit during which inguinal hernia repair is performed | | |
| Individual Participants | | | |
| Study Specific | LAR – Legally Authorized Representative | | |
| Abbreviations/ | LMA – Laryngeal Mask Airway | | |
| Definitions | ETT- Endotracheal tube | | |

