4.0 Study Endpoints

4.1 Describe the primary and secondary study endpoints.

The primary endpoint of this study will be SpO2 measured at 3 standardized timepoints.

Secondary endpoints will include:

- SpO2 less than 90%
- End tidal CO2 measurement at 3 standardized timepoints
- Peak airway pressures measured at 3 standardized timepoints

• Occurrence of laryngospasm

4.2

The safety endpoint would be conversion to general endotracheal anesthesia.

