11.0 Additional Study Activities

- Additional study activities will include secondary data use recording data from the medical record after the procedure is complete.
- **11.1** Blood and Other Specimen Collection:

1. N/A- no blood or other specimens will be collected for this study.

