16.0 Potential Benefits*

16.1 Potential benefits include:

Potentially decreased time in operating room for LMA group. Potential benefit of avoiding ETT and possible decreased risk of respiratory complications. Possible

decrease in laryngospasm, bronchospasm, and postoperative respiratory complications.

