29.0 Data and Specimen Management*

29.1 Data Management: Describe how data will be handled, including:

Data will be collected by reviewing the participant's medical record after the circumcision procedure is complete. Data will be recorded in REDCap, securely stored on the CMH servers, and only accessible to IRB-approved study team members. Data will be rolled into the Department of Surgery Data Repository (DSDR, IRB#18020079) at the time of data collection, and will remain stored in the DSDR under the approved provisions of the repository for potential use in future research studies.

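### Laryngospasm and SpO2 below 90% have no definition or observation window and are read from the chart afterwards, so an uncharted event cannot be told from no event

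*Combined protocol and SAP*

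**What the plan says.** Section 4.1 names two event endpoints among the secondary endpoints: "SpO2 less than 90" (percent) and "Occurrence of laryngospasm". Neither has a definition, an assessor, or a start and end of observation. The other secondary measurements do have a schedule, for example "End tidal CO2 measurement at 3 standardized timepoints", although the three timepoints are not themselves defined. The Study Summary (1.0) makes laryngospasm an objective, worded "Documentation of laryngospasm occurrence in both" groups, without giving a method.

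The source of the data is stated three times. Section 26.2: "Data will be obtained from the medical record after the hernia repair procedure is completed". Section 11.0: "secondary data use recording data from the medical record after the procedure is complete". Section 29.1: "Data will be collected by reviewing the participant's medical record after the circumcision procedure is complete". The last names a different operation and needs correcting in any case.

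Section 28.1 computes the incidence of complications and compares groups by chi-square. It gives no rule for missing data. No blinding of clinicians or chart abstractors is described. The Table of Events (5.2) is marked not applicable. Among the possible benefits of the LMA, 16.1 lists a "decrease in laryngospasm, bronchospasm, and postoperative respiratory complications".

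**The concern.** Laryngospasm is a bedside judgement, not a value that a monitor stores. If its only source is the chart, it enters the dataset only when someone wrote it down, and that person knew which airway was in place. Nothing in the plan requires a positive statement that no laryngospasm occurred, so the analyst cannot tell a chart that is silent because nothing happened from one that is silent because nobody wrote.

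The missing window adds a second problem. With a tube through the cords, laryngospasm during surgery is essentially excluded, and the risk in that arm lies before intubation and after extubation. With an LMA it can also occur during surgery. How far into emergence and recovery the chart is read therefore affects the two arms differently, and two abstractors could choose different stopping points.

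At stake is the secondary statement in 3.3 and 16.1 that the LMA may reduce respiratory complications. With 25 children per arm, one child is 1/25 = 4 percentage points, so one or two unrecorded events visibly change the estimate.

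**Working it through.** **The plan's own figure.** The only computed figure is the total of 50 in 28.1, which concerns mean SpO2. With n per arm = 2 × (SD/margin)² × (z_α + z_β)², margin 5, SD 5 and 90% power:
- 2.5% one-sided: 2 × 1 × (1.960 + 1.282)² = 21.0, so 22 per arm, 44 in total.
- 2.5% two-sided: 2 × 1 × (2.241 + 1.282)² = 24.8, so 25 per arm, 50 in total.

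The figure reproduces under the second reading. It says nothing about the event endpoints, for which the plan gives no rate and no power.

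**What the sections give together.**
1. Source: the medical record, read after the procedure (11.0, 26.2, 29.1).
2. Definition and window: none in 4.1. Section 5.2 supplies no schedule. Section 27.2 describes monitoring while the procedure is under way and does not mention recovery.
3. Outer limit: a single visit (1.0), with no follow-up (12.0). Section 26.1 says the data also cover the wider encounter. Recovery records may therefore be read, but nothing requires it.
4. Analysis: incidence and chi-square (28.1), with no category for not recorded.

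**Illustration of size.** True risks and capture rates are assumptions; the documents give neither. Recorded risk = true risk × capture. True risk is equal in both arms, with 25 per arm and capture of 90% in one arm and 60% in the other. Which arm has the lower capture is left open.

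| True risk | Recorded at 90% | Recorded at 60% | False difference (points) | Expected recorded events |
|---|---|---|---|---|
| 4% | 3.6% | 2.4% | 1.2 | 0.9 v 0.6 |
| 8% | 7.2% | 4.8% | 2.4 | 1.8 v 1.2 |
| 12% | 10.8% | 7.2% | 3.6 | 2.7 v 1.8 |
| 20% | 18.0% | 12.0% | 6.0 | 4.5 v 3.0 |

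With full capture in both arms the expected difference is zero.

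**Effect on the test** (exact enumeration of the uncorrected chi-square at 5%, 25 per arm):
- True risk 12% in both arms: the rejection rate is 5.3% with full capture, 6.6% with capture of 90% v 60%, and 8.1% with 90% v 50% (recorded 10.8% v 6.0%).
- True risk 4% in both arms: 1.2% with full capture and 0.8% with 90% v 60%, so no inflation.
- A real difference of 10% v 20%, with the higher-risk arm captured at 60% and the other at 90%: recorded as 0.10 × 0.90 = 9% v 0.20 × 0.60 = 12%. The ratio falls from 2.0 to 1.33, and power falls from about 17% to about 6%.

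Unequal charting thus does more harm to the estimate, and to the chance of seeing a real difference, than to the false-positive rate.

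**The case against.** The strongest reply is that the documents do not say several things a reader might infer.

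- *Blank means no event.* No section says so. Section 28.1 has no missing-data rule, which is silence and not a rule. What stands is that an incidence computed from charts, with no category for not recorded, cannot make the distinction.
- *Observation stops at the end of surgery.* Section 26.2 says when the chart is read, not when observation ends. Sections 1.0 and 26.1 allow the recovery record to be used, and the absence of follow-up in 12.0 concerns the time after the visit. What stands is that reading that record is allowed and not required.
- *SpO2 below 90% is read only at the three timepoints.* Section 4.1 attaches the timepoints to the other measurements and not to this one, so any occurrence is the more natural reading. What stands is that the plan does not say which is meant. This part is weaker than the laryngospasm part.
- *Documentation is left to chance.* The Study Summary makes documenting laryngospasm an objective and 27.2 promises close monitoring. The intention is there; the method is not.

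The capture rates above are also invented, and even 90% v 50% raises the rejection rate at 12% true risk by less than 3 points. Low power is mainly a matter of sample size: perfect recording still gives only about 17% for 10% v 20%. The plan's benefit wording is hedged. All of this stands and limits the point, but none of it supplies a definition, a window or a recording method.

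**Conclusion.** The point holds for two secondary endpoints. Neither has a definition or window, and laryngospasm rests on after-the-fact reading of an unblinded bedside judgement. The primary SpO2 comparison is not affected.

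The size of any bias is unknown. The differences of 1.2 to 6.0 points depend wholly on assumed capture of 90% v 60% and assumed true risks of 4% to 20%. A reader might conclude that the comparison is biased for or against the LMA. The documents do not support that: they show that unequal loss is possible, not that it occurs or which arm it would favour.

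The change is worth making before enrolment, because a laryngospasm that nobody charted cannot be recovered later.

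**What to change.** In 4.1 and 26.2:
1. Set one observation window for both arms, from induction to discharge from the recovery unit.
2. Give one written definition of laryngospasm.
3. Replace chart abstraction of laryngospasm with a required prospective REDCap item (yes / no / not recorded) in two parts. The anesthesia provider completes the first at hand-over, for induction through emergence. Staff already present complete the second at recovery-unit discharge, for the recovery period. A single form at hand-over would not cover the window.
4. Define SpO2 below 90% as any such reading in the anesthesia and recovery record over that window, not only at the three timepoints. Use stored monitor data if the sponsor confirms that they exist; the documents do not say.

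Bronchospasm could be added to the form, but this is optional because it is not a listed endpoint.

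REDCap is already in use (29.1), and 9.1 provides for treating providers who are study team members. The estimated cost is a minute or two per case for the treating team, with no extra visit or assessor. Two limits remain: the recorder still knows the airway, and power for rare events at 25 per arm is unchanged.

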26.3 N/A

27.0 Adverse Events and Unanticipated Problems*

27.1 Monitoring:

27.2 There are no Adverse Events or Unanticipated Problems associated with this study, as the LMA and ETT techniques being evaluated are already used in current standard care. As when these techniques are used in current standard care, the Anesthesia team will closely monitor patients during the procedure and will modify anesthesia if clinically warranted.

27.3 Reporting: We will follow Policy 5.11 Reportable Events of the CM Research Program Policies and Procedures in regards to reporting adverse events and other unanticipated problems to the CM IRB.

28.0 Statistical Analysis*

28.1 The data analysis will be a simple calculation of demographics and incidence of complications. Comparison between groups will be completed using chi square for categorical variables and t-test for continuous variables. Statistical significance will be set at p-value <0.05

We determined the targeted sample size of 50 patients using a power calculation using the following parameters: 90% power, 2.5% Type I error rate, non-inferiority limit of 5% point of SP02, no difference between treatments, and standard deviations of 1, 2, 5, and 10.

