2.0 Objectives*

2.1 Purpose, specific aims or objectives: Describe the purpose, specific aims, or objectives. If more than one objective be sure to list separately.

This study aims to evaluate the effectiveness during general anesthesia of laryngeal mask airway versus endotracheal tube for laparoscopic inguinal hernia repair.

2.2 Hypothesis: Use of laryngeal mask airway is not inferior to the use of endotracheal intubation for patients undergoing laparoscopic inguinal hernia repair.

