3.0 Background*

3.1 Describe the relevant prior experience and gaps in current knowledge.

Children undergoing laparoscopic inguinal hernia repair typically received general anesthesia with endotracheal intubation. There are limited studies looking at the use of laryngeal mask airway for short laparoscopic procedures in pediatric patients.^{1,2}

3.2 Describe any relevant preliminary data.

There are limited pediatric literature evaluating the use of laryngeal mask airway for laparoscopic procedures compared with traditional endotracheal intubation.¹ This study aims to add to this literature in providing information comparing the two techniques.

3.3 Provide the scientific or scholarly background for, rationale for, and significance of the research based on the existing literature and how it will add to existing knowledge.

The rationale for this study is to show that general anesthesia with laryngeal mask airway is an effective and non-inferior technique compared with general anesthesia with endotracheal intubation in pediatric patients undergoing laparoscopic inguinal hernia repair and may offer benefits in terms of efficiency of care and respiratory complications.

References

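### The trial asks a non-inferiority question with a 5-point SpO2 margin, but the stated analysis is an ordinary t-test or chi-square and no rule for concluding non-inferiority is given

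*Combined protocol and SAP*

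**What the plan says.** Three sections of the protocol set a non-inferiority question:

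- Section 2.2, hypothesis: "Use of laryngeal mask airway is not inferior to the use of endotracheal intubation for patients undergoing laparoscopic inguinal hernia repair".
- Section 3.3, rationale: the aim is to show that LMA anaesthesia "is an effective and non-inferior technique compared with general anesthesia with endotracheal intubation in pediatric patients".
- Section 28.1, sample size: "90% power, 2.5% Type I error rate, non-inferiority limit of 5% point of SP02", with a true difference of zero and SDs of 1, 2, 5 and 10, leading to 50 patients (25 per group in 8.1).

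The analysis text, also in 28.1, promises descriptive statistics and then: "Comparison between groups will be completed using chi square for categorical variables and t-test for continuous variables". The threshold is: "Statistical significance will be set at p-value <0.05". That is the whole analysis plan.

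On the endpoint, section 4.1 says: "The primary endpoint of this study will be SpO2 measured at 3 standardized timepoints". Nothing says which reading or summary the 5-point limit applies to. Section 4.2 adds: "The safety endpoint would be conversion to general endotracheal anesthesia". No analysis set is defined.

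**The concern.** An unqualified t-test at p<0.05 asks whether the two means differ. The hypothesis asks whether LMA is worse by less than 5 points. The margin appears only as a sample-size input, so the stated 90% power and 2.5% error belong to a test that the plan never commits to.

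Section 28.1 does not say how a t-test result will be read, and either informal reading can mislead:

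- If p≥0.05 were taken as non-inferior, a noisy trial could pass an LMA that is a full 5 points worse.
- If p<0.05 favouring ETT were taken as failure, a precise trial could reject an LMA well inside the margin.

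The first risk belongs to the larger planned SDs and the second to the smaller ones. Without a rule fixed in advance, the same data could be reported as success or as failure.

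**Working it through.** **Inputs.** From 28.1: margin 5 points, type I error 2.5%, power 90%, true difference 0, SDs 1, 2, 5 and 10. From 8.1: 25 per arm. Assumptions: the 2.5% is one-sided (28.1 does not say), SpO2 is roughly normal, and the SD is equal in both arms.

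**The plan's own figure.** n per arm = 2 × [(z₁₋α + z₀.₉₀) × SD / 5]².

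- One-sided 2.5%, SD 5: 2 × (3.2415 × 5/5)² = 21.01, so 22 per arm and 44 in total (46 by exact t).
- The other SDs, in total by exact t: 6 (SD 1), 10 (SD 2) and 172 (SD 10).
- If 2.5% is read as two-sided (1.25% per side), SD 5: 2 × (3.5230)² = 24.82, so 25 per arm and 50 in total (54 by exact t).

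The plan's 50 therefore comes out exactly only with SD 5, the second reading of alpha and the normal approximation. It is in any case a calculation against the margin.

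**Interval width.** Degrees of freedom 48, critical t = 2.0106. Half-width of the 95% CI = 2.0106 × SD × √(2/25) = 0.5687 × SD, which is 0.57, 1.14, 2.84 and 5.69 points at SDs 1, 2, 5 and 10.

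**When the t-test settles the question.** A result is non-significant when the observed difference is smaller in size than the half-width. The lowest possible CI limit is then -2 × 0.5687 × SD. This stays above -5 only if SD < 5 / (2 × 0.5687) = 4.396. So a non-significant result implies non-inferiority when the observed pooled SD is below about 4.4, and does not settle it at SD 5 or 10. A significant result favouring LMA always implies non-inferiority. A significant result favouring ETT may or may not be compatible with it. For example, at SD 2 an observed difference of -1.5 has a CI of -2.64 to -0.36, which is significantly worse yet well inside the margin.

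**Operating characteristics.** Noncentral t, 25 per arm. The margin rule is: lower 95% CI limit above -5. The last row is by simulation.

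| | SD 1 | SD 2 | SD 5 | SD 10 |
|---|---|---|---|---|
| LMA 5 worse: t-test non-significant | ~0% | ~0% | 6.6% | 59% |
| LMA 5 worse: margin rule met | 2.5% | 2.5% | 2.5% | 2.5% |
| LMA 1 worse: t-test significant, either direction | 93% | 41% | 11% | 6% |
| LMA 1 worse: margin rule met | >99.9% | >99.9% | 79% | 28% |
| No difference: margin rule met | >99.9% | >99.9% | 93% | 41% |
| No difference: non-significant but margin rule not met | 0% | 0% | 4% | 56% |

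**If all three timepoints had to meet the margin** (SD 5, no true difference). The chance of failure at one timepoint is 0.0663. Joint power is at least 1 - 3 × 0.0663 = 0.801, is 0.934³ = 0.814 if the timepoints are independent, and is 0.934 if they are perfectly correlated.

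**The case against.** The strongest reply is that 28.1 names a t-test without stating its null hypothesis or sidedness. A t-test can be run against a limit of -5, and a two-sided p<0.05 pairs naturally with a one-sided 2.5%. On that view the plan is under-specified, not wrong. It is true that no null is stated. But the same sentence covers every continuous variable, including end-tidal CO2 and peak airway pressure, for which no margin exists, so a shifted test is not what the text describes. If one was intended, writing it down is the same repair.

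Four further points have some force:

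- The largest figures come from SD 10, where 50 patients are too few under any rule: the margin rule itself has 41% power there. SD 5 is the fairer case, and the error there is 6.6% against 2.5%.
- The t-test counts at a 1-point deficit include significance in either direction. Counting only results that favour ETT gives about 93%, 41%, 10% and 5%, a change of about one point or less.
- Both harms are conditional on a reading that the plan does not state. That is so, and the absence of a stated reading is itself the defect.
- One-sided 2.5% is an assumption. It is the ordinary convention and agrees with two-sided p<0.05, but the exact match to 50 under the other reading means that the sponsor should confirm it.

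**Conclusion.** The concern holds and must be fixed before the data are analysed. The stated analysis does not test the stated hypothesis, and nothing in the protocol says what result would establish non-inferiority.

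The size of the consequence depends on the SD, which the plan leaves anywhere from 1 to 10. At SDs of 1 and 2 the danger is rejecting an LMA that is clearly inside the margin. At SD 5 the danger is a modestly inflated false pass, and at SD 10 a severe one. These figures rest on 25 analysed children per arm, a one-sided 2.5% error, approximate normality, and the listed SDs applying to whichever SpO2 measure is made primary. The mismatch itself rests on none of these assumptions.

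**What to change.** Replace the primary-analysis text in 28.1 with a paragraph such as this:

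> The primary SpO2 measure is [one named timepoint or summary of the three readings]. The mean difference, LMA minus ETT, will be estimated with its two-sided 95% confidence interval. LMA will be declared non-inferior only if the lower limit is above -5 percentage points (one-sided 2.5%). Children will be analysed as randomised, including LMA children converted to ETT, with a per-protocol analysis in support. A non-significant difference will not be taken as evidence of non-inferiority.

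Keep two-sided p<0.05 tests for the secondary comparisons.

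Two decisions are needed before analysis:

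- **Primary measure.** Each child's lowest of the three readings is one possibility. Whatever is chosen, confirm that the 5-point margin and the assumed SD make sense for it. Alternatively, require all three timepoints to meet the margin. That needs no alpha adjustment, but at SD 5 power falls from 93% to somewhere between 80% and 93%.
- **Analysis set.** Conversion from LMA to ETT can pull the arms together and so favour non-inferiority, which is why the per-protocol analysis should accompany the as-randomised one.

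The cost is one paragraph and these two decisions, with no new data. Fifty patients keep at least 90% power for this rule on a single measure up to an SD of about 5.3. At SD 10 the total needed would be 172.
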